We will undertake a prospective, interventional, non-randomised, implementation study of mPOCT for COVID-19 in adults presenting to University Hospital Southampton NHS Foundation Trust. A brief validation and training phase will be followed by the post-implementation phase where patients will be recruited and tested at the point-of-care using the QIAstat-Dx Respiratory SARS-CoV-2 Panel. We will initially test patients suspected of COVID-19 based on current PHE case definitions and then progress to testing all patients with ARI as the outbreak becomes more widespread in the UK and the risks of admitting patients to hospital with unsuspected COVID-19 are high. Clinical and infection

control teams will be informed of these results in real time. The control group will consist of patients who were tested for SARS-CoV-2 by laboratory PCR but not recruited to the study during the same time period. This allows us to have a comparable control group as the outbreak progresses and hospital pathways change, as opposed to a pre-implementation group which predominantly is expected to consist of community-based patients tested in hospital for containment reasons. Only anonymised, routinely collected hospital data will be obtained for the control group. Outcome measures will be by assessed by retrospective case note analysis and will include: time to result, time in isolation facilities, detection of COVID-19 cases not initially suspected (based on current PHE case definition), antibiotic use, antiviral use, length of hospital stay, ward closures and hospital resource use. Multivariate analysis will be used to control for the effect of confounding variables between the groups.

Potential benefits to patients and the NHS

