We hypothesise that the use of a routine mPOCT for respiratory viruses including SARS-CoV-2 in adults presenting to hospital with suspected COVID-19 and/or ARI will dramatically reduce the time from patient presentation to results, compared to the current standard of PHE laboratory RT-PCR. We expect that timely detection or exclusion of COVID-19 will lead to improvements in early directed isolation facility and enhanced PPE use or de-isolation/de-escalation, in addition to other potential benefits such as reduced length of stay, improved use of antibiotics and antivirals and resource use and cost for the NHS. The detection of COVID-19 positive cases presenting to hospital and not initially suspected based on current the PHE case definition will prevent widespread nosocomial transmission of SARS-CoV-2 and associated hospital ward closures.

3. Abbreviations and Definitions

AE: Adverse Event AMU: Acute medical unit ARI: Acute respiratory illness CES: School of Clinical and Experimental Sciences, Faculty of Medicine University of Southampton **CI:** Chief Investigator COVID-19: Coronavirus disease 2019 CRF: Case Report Form ED: Emergency Department GICU: General Intensive Care Unit HRA: Health Research Agency ICU: Intensive care unit mPOCT: Molecular Point-of-Care test PCR: Polymerase Chain Reaction PHE: Public Health England PI: Principal Investigator POCT: Point-of-Care Test **PPE: Personal Protective Equipment REC: Regional Ethics Committee** RHDU: Respiratory High Dependency Unit RT-PCR: Reverse Transcriptase Polymerase Chain Reaction SAE: Serious Adverse Event

SARS-CoV-2: Severe acute respiratory syndrome coronavirus 2

UHS: University Hospital Southampton NHS Foundation Trust

WHO: World Health Organisation

4. Introduction

COVID-19

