1. To assess the clinical impact of mPOCT for respiratory viruses including SARS-CoV-2 on outcomes measures including: time to test result, time in COVID-19 assessment cohort areas, time to definite ward move, length of stay in hospital, use of antibiotics, use of antivirals, ward closures, and hospital resource use, in adults hospitalised with ARI.

2. To assess the implementation feasibility of mPOCT for COVID-19.

3. To assess the ease-of-use, reliability and real-world diagnostic accuracy of the QIAstat-Dx SARS-2-CoV assay, , using respiratory samples prospectively collected from adults presenting to hospital with ARI, compared to the reference standard of PHE laboratory RT-PCR for SARS-CoV-2.

6. Recruitment and Study Processes

Overview

This is a non-randomised, controlled, implementation study of mPOCT for respiratory viruses including COVID-19 with prospective recruitment for participants in the intervention phase. The intervention consists of testing respiratory samples from patients at the point-of-care using the QIAstat-Dx Respiratory SARS-CoV-2 Panel. In the contemporaneous control group, routinely collected data on outcomes in patients tested for COVID-19 using laboratory RT-PCR, including time to test result. In the intervention phase patients will be tested using the QIAstat-Dx Respiratory SARS-CoV-2 Panel with results delivered immediately to the clinical and infection control team and outcome and diagnostic accuracy data collected retrospectively. A brief validation phase will precede the intervention phase. Study processes that patient-participants undergo in intervention phase are summarised in Figure 1.

[figure not shown]

Figure 1: Participant flow through the study

POCT = point-of care test

*if lacks capacity to consent, participant's consultee may be substituted here

Control group

Patients (≥18 years old) presenting to hospital with ARI who have been tested for SARS-CoV-2 during the same time period as part of standard clinical care (but not included in the intervention) via University Hospital Southampton NHS Foundation Trust (UHS) will be identified via (laboratory) information management system and select clinical data will be obtained by electronic records including age, sex, co-morbidity, observations, blood test results, length of hospital stay, and time to test result. Consent is not obtained for these patients, and only anonymised data already collected as part of routine clinical care will be used.

Screening

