Non-hospitalised hospital staff members may be included in the intervention phase of the study, if they satisfy the other inclusion & exclusion criteria. The same consent and study procedure processes are followed. However, their results will not be included in analyses of most outcome measures, with the exception of time to result. Days away from work may be used as an additional outcome measure.

Participant Withdrawal

A participant, or their consultee where a participant lacks capacity, may decide to withdraw from the study at any time, without giving reason, and with no detriment to their medical care or legal rights.

The chief investigator may withdraw a patient from the study in the interests of participant safety or the integrity of the research study, or on the advice of the sponsor's representative (R&D department).

Any patient, or their consultee where a patient lacks capacity, who is withdrawing from the study has the options withdraw and have data and/or samples collected so far retained, or withdraw and have their data and/or samples destroyed (but signed consultee declaration forms, minimal personal identifiable information to record the withdrawal, and any completed point-of-care test result will be retained). Although the study procedures are very brief, if a patient loses capacity after enrolment but before the study procedures are completed, consultee consent must be sought to continue with any study procedures, or the participant must be withdrawn.

A note to file would normally be sufficient to record any withdrawal.

7. Outcomes

Primary outcome

• The primary outcome measure is the time from COVID-19 test being requested to the result being available to clinical teams.

Secondary Outcomes

- The time from presentation to hospital to COVID-19 test result
- Time spent in COVID-19 assessment cohort area
- Time to definitive ward move
- Number of bed moves •
- Duration of hospitalisation •
- Number and proportion of clinically unsuspected COVID-19 positive patients detected •
- Proportion of patients treated with antibiotics
- Proportion of patients treated with single doses or brief courses (<48 hours) of antibiotics •
- Duration of antibiotic use, days
- Proportion of all influenza antiviral use occurring in influenza positive patients •
- Proportion of all influenza antiviral use occurring in influenza negative patients •
- Time from admission to influenza antiviral commencement

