Summaries of all baseline characteristics will be presented using means and standard deviations, medians and interquartile ranges, or frequencies and percentages, as appropriate. The groups will be compared using chi-square tests for equality of proportions for binary data (e.g. proportion of cases of influenza detected) and using independent-samples t-tests or non-parametric equivalent as appropriate for continuous data (e.g. duration of isolation facility use, etc.).

The primary outcome measure (median duration of isolation facility use) will be compared between the groups using the Mann-Whitney U test. Multivariate analysis will be performed to adjust for confounding variable in view of the non-randomised nature of the study.

12. Safety

Serious Adverse Events

The risks of respiratory tract sampling and additional blood tests being taken are minimal and where occurring are likely to be mild. No additional adverse events related to mPOCT for respiratory viruses including COVID-19 are anticipated. However active monitoring and reporting of severe adverse events will be undertaken. A Serious Adverse Event (SAE) is any adverse event that:

- Results in death

- Is life-threatening

- Requires hospitalisation or prolongation of existing hospitalisation

- Results in persistent or significant disability or incapacity
- Consists of a congenital anomaly or birth defect

In the event of a SAE, a study doctor will consider the likelihood of the event being related to the study based on the documented evidence from the treating clinicians. SAEs will be reported via the sponsor's standard forms and processes. SAEs will be reported within 24 hours of the study team learning of the SAE. In the event of a SAE, the PI will be involved in deciding whether this was a study-related event. In the event of a study-related SAE, the REC will be informed as per HRA regulations.

Participants already admitted to AMU, or another hospital ward including high dependency or an intensive care unit, or are in ED but with a decision already made to admit, are considered already hospitalised. However, an adverse event leading to prolongation of their existing hospitalisation will be counted as an SAE.

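### Section 11 assigns the primary test to isolation duration, but Section 7 defines the primary outcome as time from test request to result

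*Protocol*

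**What the plan says.** Section 7 (Outcomes, Primary outcome) gives one definition: "The primary outcome measure is the time from COVID-19 test being requested to the result being available to clinical teams".

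Section 11 (Statistical Analysis Plan) gives another: "The primary outcome measure (median duration of isolation facility use) will be compared between the groups using the Mann-Whitney U test". The next sentence adds a multivariate analysis to adjust for confounding, because the groups are not randomised.

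Just before that, Section 11 sets a general rule for continuous variables and uses the same isolation measure as its example: "independent-samples t-tests or non-parametric equivalent as appropriate for continuous data (e.g. duration of isolation facility use, etc".

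Section 11 also ties a missing-data rule to the primary outcome: multiple imputation is to be considered if more than 5% of values are missing for that outcome or for key secondary outcomes.

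**The concern.** A protocol should carry one primary outcome from its definition through to its test. Here the definition and the test refer to different quantities. Test turnaround depends on the assay and the route by which results are delivered. Time in isolation depends also on room availability and infection-control decisions made after the result. A difference in one does not establish a difference in the other, so the two would support different headline claims.

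Section 11 is the only text that tells the analyst which test belongs to the primary outcome. Taken literally, it directs that test to the wrong variable. Request-to-result time is then left to the general rule for continuous data, which offers a t-test or a non-parametric alternative as appropriate. The study is open and not randomised, so the primary analysis should be unambiguous before the outcome data are examined.

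**Working it through.** No arithmetic applies. The protocol states no significance level, power, effect size or standard deviation for either outcome. The sample size of 500 per group rests on kit supply, so it cannot show which outcome was meant. The check is a comparison of the places that mention either measure.

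**Where request-to-result time, or time to result, appears**
- Section 7, Primary outcome: defined as the primary outcome.
- Section 5, Objective 1: test-result time heads the list, "time to test result, time in COVID-19 assessment cohort areas, time to definite ward move, length of stay in hospital". Isolation duration is not in that list.
- Section 6, Control group: the data to be extracted include "age, sex, co-morbidity, observations, blood test results, length of hospital stay, and time to test result". Time to result is named and isolation is not.
- Section 8: time to results comes first among the outcomes that 500 patients are said to be enough to assess.
- Section 9: turnaround time of respiratory virus results is to be collected in each group.
- Section 2, Methods: listed first among the outcome measures, without being marked as primary.

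**Where duration of isolation appears as an outcome**
- Section 2, Methods: "time to result, time in isolation facilities, detection of COVID-19 cases not initially suspected". Both measures are in this list and neither is marked as primary.
- Section 11: once as the example of an ordinary continuous variable, and once as the primary outcome.
- Section 7: absent. The nearest entry is a secondary outcome, "Time spent in COVID-19 assessment cohort area", which measures time in a cohort area and not use of isolation facilities.
- Section 9: use of side rooms and time until isolation are named, but the duration of isolation is not.

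The data lists in Sections 6 and 9 are introduced as inclusive, so silence about isolation duration does not prove that it will not be collected. It does mean that no passage shows it being captured in the control group.

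**Result.** The two statements cannot both be true of one primary outcome. Section 7 has the support of the objectives, the control-group data, the sample-size text and the data collection. The Section 11 label has support only from the unranked Overview list. Section 11 itself also treats isolation duration as a routine continuous variable one sentence before calling it primary.

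**The case against.** The best reply is that a careful reader can tell what was meant. Section 7 is the designated place for outcomes, the rest of the protocol agrees with it, and the Section 11 sentence looks like text that was not updated, although the document does not say so. The analysis is also to be done by a statistician independent of the study team. This reply stands in part: it shows which way to correct the text. It does not remove the error, because the one sentence that specifies the primary test still names another variable.

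A reader might infer more than the protocol supports:

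- **That no confirmatory claim is defined at all.** Too strong. Section 7 defines one and the surrounding text supports it.
- **That there is a third competing primary.** Section 2 hypothesises that testing "will dramatically reduce the time from patient presentation to results, compared to the current standard of PHE laboratory RT-PCR". That paragraph lists several expected benefits and ranks none as primary, and presentation-to-result time is an explicit secondary outcome in Section 7.
- **That the false-positive rate rises by a known amount.** Two independent tests at 5% would give 1 − 0.95² = 9.75%, and three would give 1 − 0.95³ = 14.3%. The protocol states no significance level, and the outcomes come from the same patients, so independence cannot be assumed. The calculation also requires every null hypothesis to be true. That is hard to credit for turnaround, with a panel taking about 1 hour set against the 3 to 4 days from sampling to result that Section 4 reports for laboratory testing at the time of writing.
- **That up to 24 hours of delay is hidden in the intervention group.** The 24 hours is an eligibility limit, not a distribution of delays, and a 12-hour mean would need uniform recruitment over that window. The protocol does not say when a point-of-care request is logged. Controls may also wait between presentation and request, and the presentation-to-result secondary outcome shows such delay in both groups.

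The missing-data consequence is also modest. The 5% trigger covers key secondary outcomes too, and imputation is only to be considered.

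**Conclusion.** The contradiction is real and should be corrected before analysis. As written, Section 11 would apply the primary test to an endpoint that is not the defined primary outcome and is not in the Section 7 list. The consequence is one of kind: the wrong variable in the only sentence that specifies the primary test, with a secondary effect on the missing-data trigger. No error rate or hidden delay can be attached to it from the protocol.

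The conclusion rests on reading the two sentences as they stand. It does not depend on a separate statistical analysis plan, since both are in the protocol and conflict there. That Section 7 is the intended definition is a judgement from the weight of the other sections, and the sponsor should confirm it.

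**What to change.** In Section 11, replace the parenthetical description of the primary outcome with the Section 7 definition, time from COVID-19 test request to result available to clinical teams. Keep the Mann-Whitney U test for it, with the adjusted analysis already planned. Then either add duration of isolation facility use to the secondary outcomes in Section 7 or delete it as an outcome from Sections 2 and 11. Make the change before the data are analysed and record its date.

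The cost is a one-sentence correction plus one line for isolation duration. The primary outcome needs no new kind of data, since turnaround is already to be collected in each group. If isolation duration is kept, the team should confirm that it can be obtained for controls as well, because no data list names it. The definition of the request time in Section 7 need not change for this correction.

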Currently, all diagnostic testing for COVID-19 (SARS-CoV-2) in the UK is takes place in the PHE reference laboratory in Colindale, London, with testing capability being rolled out to regional PHE laboratories in late February 2020. Testing utilises RT-PCR and is thought to be highly accurate but the current diagnostic pathways are unacceptably slow; the time from sampling to results being available is currently around 3-4 days. Even when laboratory testing is rolled out to regional PHE laboratories the turnaround time for results is still likely to be too slow to allow clinical decision making in a meaningful timeframe for clinical and infection control teams. Currently there are small numbers of suspected cases of COVID-19 in the UK and the vast majority of specimens test negative. Suspected cases currently have to spend several days in hospital isolation facilities with staff using full enhanced personal protective equipment (PPE) or self-isolating at home, until results are returned. It is likely

that there will be many more suspected cases of COVID-19 over the coming weeks with high numbers of patients presenting to secondary care and therefore requiring enhanced isolation facility use and testing. In this context the additional resource demand on secondary care and laboratories will be immense and the current diagnostic pathway will be unsustainable.

The current case definition for suspected cases of COVID-19 relies on a recent history of travel to heavily affected areas in Asia and elsewhere. However as the virus is highly contagious, mainly causes mild illness and can even be transmitted by minimally symptomatic patients [5], clusters of infected patients are likely to go unrecognised as the outbreak progresses. There is therefore a high risk of COVID-19 cases that do not fulfil the case definition and so are clinically unsuspected, being hospitalised in the coming weeks. If these are not tested and appropriate isolation facilities used at presentation then widespread nosocomial transmission in hospitals is likely to occur, with devastating consequences for patients and hospitals. There is therefore a compelling argument as the outbreak spreads, for routine testing for SARS-CoV-2 in all patients presenting to hospital with compatible clinical symptoms (i.e. acute respiratory illness) alongside syndromic testing for other respiratory viruses.

Molecular POCT for respiratory viruses

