Accepting that the prevalence of COVID-19 during the study is highly speculative at present, and so formal samples size calculation for diagnostic accuracy studies are not possible, testing 500 patients will allow us to make an ongoing assessment of the real-world diagnostic accuracy of the QIAstat-Dx Respiratory SARS-CoV-2assay compared to the current reference standard of laboratory PCR testing using the PHE RdRP assay.

The control group will be 500 patients for an adequate comparison.

9. Data collection

Demographic and clinical data will be collected for all patients at enrolment including: age, sex, ethnicity, smoking status, vaccination status, co-morbidities, medication use, symptoms, duration of illness prior to hospitalisation, observations (pulse rate, respiratory rate, blood pressure, oxygenation status), laboratory results, radiology results, antimicrobial and antiviral use prior to hospitalisation and provisional diagnosis. Data will be recorded on a Case Report Form, which we intend to be electronic (ALEA). Once patients have been discharged or after 30 days (whichever is soonest), clinical data will be collected retrospectively from electronic and physical case notes including: use of antivirals, duration of antivirals, time from assessment to antiviral use, use of side room facilities, time from assessment to isolation facility use, time to clinical stability, duration of supplementary oxygen use, duration of hospitalisation, complications including ICU and RHDU admission, representation and readmission to hospital within 30 days, final diagnosis and mortality. The number of diagnostic tests and procedures performed will also be recorded and data will also be collected on the turnaround time of respiratory virus test results in each group.

10. Data Management

The subjects' anonymity will be maintained. The study team will keep a log of each subject's name, hospital ID number, date of birth, and unique participant trial number. The participant details will be recorded on the secure NHS Edge system in a similar manner, including NHS number. This participant trial number is used on documents after screening to maintain confidentiality. Documents that are not anonymous (e.g. signed informed consent forms) will be maintained separately, in strict confidence.

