The study staff will be responsible for entering study data in the Case Report Form (CRF). It is the investigators' responsibility to ensure the accuracy of the data entered in the CRF.

Only the research study team will know the identity of subjects and have access to the list linking participant details to the participant trial number.

Essential Document Retention

Essential documents, as defined by ICH GCP, include all signed protocols and any amendment(s), copies of the completed CRFs, signed informed consent forms from all subjects who consented, hospital records, and other source documents, REC approvals and all related correspondence including approved documents, study correspondence and a list of the subjects' names.

The investigator and/or sponsor must retain copies of the essential documents for a minimum period following the end of the study. This period is defined by local guidelines where the research is being conducted. For all subjects that are entered into the study, the medical notes and electronic systems may be marked in line with local R&D guidelines to alert other users of the notes and systems to the patient's enrolment in this study.

The chief investigator is responsible for, with the sponsor, ensuring that documents are archived in accordance with local NHS R&D procedure at study close. Documents are expected to be archived for 15 years.

Data monitoring

On the basis of the very low risk of harms associated with the intervention in this non-CTIMP trial, no data monitoring committee or interim analysis is planned.

11. Statistical Analysis Plan

Trial results will be reported in accordance with the Consolidated Standards of Reporting Trials (CONSORT) statement. Statistical analysis will be performed by a dedicated medical statistician from the University of Southampton, independent from the study team ([name]). No interim analysis is currently planned.

Patients in the groups will be compared using standard descriptive and comparative statistical methods using Prism version 7.0 (GraphPad Software Inc; La Jolla, California), and Stata version 16 (StataCorp, College Station, Texas) or more updated software versions where available.

Missing data was minimal (<2%) in the Cl's previous POCT studies and therefore is not expected to be significant issue in this trial. The use of multiple imputation will be considered should missing data exceed 5% for the primary outcome or for key secondary outcomes.

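### Calendar time can be confounded with group: the primary test is an unadjusted Mann-Whitney, and no rule fixes which 500 contemporaneous controls are taken

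*Protocol*

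**What the plan says.** Section 11 gives one test for the primary outcome, which "will be compared between the groups using the Mann-Whitney U test". The next sentence reads "Multivariate analysis will be performed to adjust for confounding variable in view of the non-randomised nature of the study". It names no model and no calendar term, and does not say whether the adjusted or the unadjusted result leads.

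Controls are adults tested for SARS-CoV-2 in routine care over the same period and not recruited (section 2, Methods; section 6, Control group). They are found through the laboratory information system. Section 8 says only "The control group will be 500 patients for an adequate comparison". No section says whether these are all, consecutive, random or date-matched patients. Recruitment may run for up to 6 months (section 6, Intervention phase).

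The protocol expects change. Section 4 says of the central laboratory pathway that "the time from sampling to results being available is currently around 3-4 days" and describes a roll-out to regional laboratories. Section 2 says "We will initially test patients suspected of COVID-19 based on current PHE case definitions and then progress to testing all patients with ARI", and justifies contemporaneous controls by the changes expected in the outbreak and in hospital pathways.

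The primary outcome is stated in two ways. Section 7: "The primary outcome measure is the time from COVID-19 test being requested to the result being available to clinical teams". Section 11 attaches the Mann-Whitney to a different variable: "The primary outcome measure (median duration of isolation facility use".

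**The concern.** Sharing a window of up to 6 months does not balance the weeks within it. Intervention recruitment follows kit supply and staffing, while routine laboratory testing follows the epidemic and testing policy. If the two groups are spread differently over the weeks and the outcome drifts, an unadjusted comparison mixes the effect of the test with the effect of the date. Outcomes are collected retrospectively from records, so an unspecified choice of 500 could also be made with results in view. Which controls are used is a design matter that the protocol itself should settle. At stake are the size of the reported benefit and, for outcomes with modest differences, whether an effect appears at all.

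**Working it through.** **Stated sample size.** The 500 per group comes from kit supply (section 8), so there is no power calculation to reproduce. At an assumed two-sided 5% level and 80% power, 500 per group detects a standardised difference of (1.960 + 0.842) × √(2/500) = 0.177. For a Mann-Whitney it is 0.177/√0.955 = 0.181, or a Mann-Whitney probability of 0.5 + 2.802 × √(1001/(12 × 500 × 500)) = 0.551. Small systematic shifts can therefore reach significance.

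**Inputs.** From the protocol: 500 per group, up to 6 months (taken as 26 weeks), 3–4 days for the central laboratory (midpoint 84 h), about 1 h for the point-of-care result. Assumed: log-normal times with log-SD 0.5; a median falling from 84 to 24 h, from 48 to 24 h, or staying at 84 h; intervention patients uniform over weeks; controls uniform or later on average; a 2 h median from request to point-of-care result.

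**No true effect (500 simulated trials per row).** Both groups follow the same trend.

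| Trend in median | Controls later by (weeks) | Unadjusted Mann-Whitney rejects | Week-stratified (van Elteren) rejects | Spurious median shift |
|---|---|---|---|---|
| 84→24 h | 0 | 6.6% | 5.2% | 0 h |
| 84→24 h | 1.1 | 32% | 4.8% | 2.8 h |
| 84→24 h | 2.2 | 80% | 5.4% | 5.2 h |
| 84→24 h | 4.2 | 100% | 4.4% | 9.2 h |
| 48→24 h | 0 | 5.2% | 4.4% | 0 h |
| 48→24 h | 1.1 | 15% | 3.4% | 1.1 h |
| 48→24 h | 2.2 | 44% | 5.4% | 2.1 h |
| 48→24 h | 4.2 | 94% | 4.4% | 3.8 h |
| flat 84 h | 0 to 4.2 | 4.4–6.0% | 4.6–5.4% | about 0 h |

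The simulation error at a true 5% is √(0.05 × 0.95/500) ≈ 1 percentage point.

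**Hand check.** Under 84→24 h the log median falls by ln(84/24)/25 = 0.0501 a week. Weeks uniform over 26 have SD √((26² − 1)/12) = 7.5, so the total log-SD is √(0.5² + (0.0501 × 7.5)²) = 0.625. A 2.2-week shift gives a standardised difference of 2.2 × 0.0501/0.625 = 0.176. That is almost exactly the difference detectable with 80% power, which agrees with the 80% in the table.

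**Real effect on time to result (100 simulated trials each).** With 2 h against a laboratory median falling from 84 to 24 h, every trial rejects under both tests. The median difference is 43 h with no shift (check: √(84 × 24) − 2 = 42.9). It is 34 or 55 h with controls about 4 weeks later or earlier, and 26 or 68 h with controls about 9 weeks later or earlier.

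**Two-period illustration.** Let a share p of controls have median 84 h and the rest 36 h, both log-normal with log-SD 0.4. The control median m solves p·Φ((ln m − ln 84)/0.4) + (1 − p)·Φ((ln m − ln 36)/0.4) = 0.5. This gives m = 40.5, 55.0 and 68.8 h at p = 20%, 50% and 70% (check at 50%: √(84 × 36) = 55.0). Relative to p = 20%, the differences are 14 and 28 h. Replacing 36 h by 60 h or 24 h makes the full spread 12 h or 40 h.

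**Why a main-effects regression does not help.** With intervention patients 50% early and a 2 h point-of-care median, median regression on group plus an early/late term gives −38.8, −53.3 and −66.6 h at control early shares of 20%, 50% and 70%. The unadjusted figures are −38.4, −53.4 and −67.0 h. The true difference is larger early than late, so one group coefficient still follows the control mix. Weighting controls to the intervention group's 50% gives 55.0 − 2 = 53 h whatever the mix.

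**The case against.** The strongest reply is that controls are contemporaneous by design, and section 2 chose them because pathways change. Confounding needs different weekly distributions in the two groups, and no passage says they differ. With equal distributions the unadjusted test keeps its level even under a steep trend. This stands: a reader might infer that calendar time is confounded with group, but the protocol supports only that it can be.

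A reader might also infer that the headline p-value for time to result is in doubt. It is not: about 1 h against a far longer laboratory time is significant under any plausible mix.

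Nor is the 14 to 28 h illustration an estimate of bias in this study. The 36 h median and the early shares are assumptions. The synopsis describes controls as tested in the regional laboratory, and section 4 dates the regional roll-out to late February 2020, before the study starts. The share of controls on the 3–4 day pathway may be nil.

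The staged widening of eligibility appears in section 2 only; section 6 has all patients with acute respiratory illness approached once the intervention phase begins. The drift argument should therefore not lean on it alone.

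Finally, section 11 does promise adjustment, and the covariate list, the model and the scope of the imputation trigger may sit in an analysis plan not shown. Those are no finding here. What remains is fixed, or left loose, in the protocol itself: an unadjusted test as the named primary comparison, and no rule for choosing controls.

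**Conclusion.** The point holds as a risk that the design leaves open, not as an established bias. An average calendar difference of 2 weeks between groups is enough to raise the false-positive rate of the unadjusted test to about 80% under an 84→24 h trend, or 44% under 48→24 h. With no trend or no calendar difference there is no problem.

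For time from request to result, the consequence is a benefit of the wrong size (43 h becoming 34 or 55 h for a 4-week shift), with direction and significance unchanged. For outcomes with smaller differences, such as length of stay or isolation time, it could create or hide an effect. Isolation time is the variable to which section 11 attaches the primary test, so the conflict with section 7 decides how serious the risk is for the primary analysis.

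The trend end points, log-SD, calendar shifts and 2 h point-of-care time are assumptions; only 84 h, as the midpoint of 3–4 days, rests on the protocol. The change should be made: it is cheap and removes the dependence on calendar mix.

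**What to change.** 1. Reconcile sections 7 and 11 so that one primary outcome is named throughout.
2. State the control selection rule by test date. Either take all eligible controls and weight them to the intervention group's calendar weeks, or have the independent statistician draw 500 at random, blind to outcomes and frequency-matched by week of test.
3. Make a week-stratified or week-weighted comparison primary, for example a van Elteren test with a week-standardised median difference and 95% confidence interval. Keep the unadjusted Mann-Whitney as supportive. Use the same week handling for length of stay and the other comparative outcomes.
4. Do not rely on main-effects median regression for calendar time, because the group difference itself varies over the period.

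Week matching deals with calendar time only; the promised multivariate analysis is still needed for patient-level confounders. The cost is some wording, a short sampling or weighting script using test dates from the laboratory system, and slightly wider intervals.
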